The primary endpoint of HbA1c will be analyzed by fitting a constrained longitudinal data analysis model with terms for treatment, visit, treatment by-visit interaction and menopausal status randomization stratum. Least-squares means and 95% confidence intervals will be used to estimate the treatment effect (difference between ertugliflozin and placebo) at the primary time point of Week 26. The two-sided p-value will also be provided for testing the significance of the difference between treatment groups.

The two primary hypotheses, comparisons of each ertugliflozin dose to placebo, will be tested sequentially to control the overall Type I error rate at 0.05. The 15 mg dose will be tested first, and the 5 mg dose will be tested if and only if a statistically significant result is achieved for 15 mg.

Analysis of Secondary Endpoints:

The proportion of subjects with an HbA1c <7% (53 mmol/mol) at Week 26 will be analyzed using a logistic regression model with terms for treatment (categorical) and Baseline HbA1c (continuous). Summary measures from the analysis will include the odds ratio, 95% confidence interval for the odds ratio, and p-value for the comparison of treatment groups.

The secondary endpoints of FPG, body weight, systolic blood pressure and diastolic blood pressure will be analyzed separately by fitting constrained longitudinal data analysis models similar to that used for the primary endpoint.

The secondary efficacy endpoints of FPG, proportion of subjects achieving an HbA1c <7%, body weight, systolic blood pressure and diastolic blood pressure will be tested for each ertugliflozin dose versus placebo using a multiple testing procedure that strongly controls the overall Type I error rate at 0.05.

Analysis of BMD

The changes in BMD from Baseline to Week 26 at the lumbar spine, femoral neck, total hip, and distal forearm will be safety endpoints. A BMD analysis set will be defined to include

all randomized subjects who have received at least one dose of investigational product and have at least one observation of BMD at any time during Phase A of the trial, including Baseline and post-Baseline time points. For analyses of changes in BMD, measurements obtained post glycemic rescue therapy will be utilized if available; however BMD measurements will be censored at the point of a subject taking BMD rescue therapy.

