1.3. Efficacy of Ertugliflozin

In Phase 2 clinical studies, subjects received ertugliflozin for up to 12 weeks in duration. Phase 2 results demonstrated that ertugliflozin significantly lowered HbA1c, blood pressure and body weight without increasing the risk of hypoglycemia. In study B1521006 involving adult subjects with T2DM who were receiving metformin monotherapy, the following placebo-adjusted mean (80% confidence interval [CI]) reductions in HbA1c (%) were observed for the 5 mg, 10 mg and 25 mg daily doses after 12 weeks of treatment: -0.69 (-0.89 to -0.49), -0.62 (-0.82 to -0.42) and -0.72 (-0.93 to -0.52) respectively. The placebo-adjusted mean (80% CI) reductions in body weight (%) for the 5 mg, for the 10 mg and for the 25 mg doses were: -1.75 (-2.35 to -1.14), -2.15 (-2.76 to -1.54) and -1.91 (-2.52 to -1.30) respectively. The placebo-adjusted mean reductions in systolic blood pressure (mmHg) seen with doses of 5 mg, 10 mg and 25 mg were: -3.69 (-6.44 to -0.93), -2.77 (-5.59 to 0.05) and -2.77 (-5.56 to 0.02) respectively; and the placebo-adjusted mean reductions in diastolic blood pressure for the 5 mg, 10 mg and 25 mg doses were: -2.03 (-3.68 to -0.37), -4.12 (-5.81 to -2.42) and -2.40 (-4.08 to -0.73) respectively.

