9. DATA ANALYSIS/STATISTICAL METHODS

Detailed methodology for summary and statistical analyses of the data collected in this trial will be documented in a Statistical Analysis Plan (SAP), which will be maintained by the sponsor. This document may modify the plans outlined in the protocol; however, any major modifications of the primary endpoint definition and/or its analysis will also be reflected in a protocol amendment.

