9.2. Efficacy Analysis

The primary analysis population for efficacy analyses will be the Full Analysis Set (FAS), which is defined separately for each analysis endpoint to include all randomized subjects who have received at least one dose of investigational product and have at least one measurement of the respective endpoint at any time during Phase A of the trial including baseline and post-baseline time points. The post-glycemic rescue therapy data from subjects who require rescue therapy prior to week 26 will be censored from primary and secondary endpoint efficacy analyses.

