9.2.1. Analysis of Primary Endpoint

The primary endpoint of HbA1c will be analyzed using a constrained longitudinal data analysis (cLDA) model with the following terms:

- Treatment (categorical),
- Visit (categorical),
- Treatment by visit interaction,
- Menopausal Status randomization stratum.

This model assumes a common mean across treatment groups at baseline and a different mean for each treatment at each of the post-baseline time points. In this model, the response vector consists of baseline and the values observed at each post-baseline time point.¹⁶ Time is treated as a categorical variable so that no restriction is imposed on the trajectory of the means over time. No explicit imputation of missing assessments will be performed. The treatment difference between each dose of ertugliflozin and placebo in terms of mean change from baseline at the primary time point of Week 26 will be estimated and tested from this model using least-squares means and 95% confidence intervals. The two-sided p-value will also be provided for testing the significance of the difference between treatment groups. An unstructured covariance matrix will be used to model the correlation among repeated measurements. The Kenward-Roger adjustment will be used with restricted (or residual) maximum likelihood (REML) to make proper statistical inference.

Sensitivity analyses will be performed to assess the robustness of the primary model. ANCOVA will be conducted utilizing the last observation carried forward as the dependent variable and including fixed factors for treatment (categorical), randomization stratum (categorical), and baseline value (continuous). A per protocol analysis will also be pre-specified in the statistical analysis plan. Descriptive and graphical summaries by treatment group and time point will also be presented. Other additional analyses to explore the robustness of results to regions and other factors will also be performed.

The two primary hypotheses, comparisons of each ertugliflozin dose to placebo will be tested sequentially to control the overall Type I error rate at 0.05. The 15 mg dose will be tested first, and the 5 mg dose will be tested if and only if a statistically significant result is achieved for 15 mg.

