9.2.2. Analysis of Secondary Endpoints

The proportion of subjects achieving an HbA1c <7% (53 mmol/mol) at Week 26 will be analyzed using a logistic regression model with terms for treatment (categorical), Baseline HbA1c (continuous). Summary measures from the analysis will include the odds ratio, 95% confidence interval for the odds ratio, and p-value for the comparison of treatment groups.

The secondary endpoints of fasting plasma glucose, body weight, systolic blood pressure and diastolic blood pressure will be analyzed separately by fitting constrained longitudinal data analysis models similar to that used for the primary endpoint. Sitting blood pressure collected in triplicate will be used for assessment of blood pressure as a secondary endpoint.

The secondary efficacy endpoints of FPG, proportion of subjects achieving an HbA1c <7%, body weight, systolic blood pressure and diastolic blood pressure will be tested for each ertugliflozin dose versus placebo using a multiple testing procedure that strongly controls the overall Type I error rate at 0.05. A step-down hierarchical, sequential testing approach will be used, as follows:

| Order | Endpoint (Change from Baseline to Week 26*) | Arm Comparison |
|---|---|------------------------------------|
| 1 | HbA1c | 15 mg ertugliflozin arm to placebo |
| 2 | HbA1c | 5 mg ertugliflozin arm to placebo |
| 3 | FPG | 15 mg ertugliflozin arm to placebo |
| 4 | FPG | 5 mg ertugliflozin arm to placebo |
| 5 | Body Weight | 15 mg ertugliflozin arm to placebo |
| 6 | Body Weight | 5 mg ertugliflozin arm to placebo |
| 7 | HbA1c <7.0% at Wk 26 | 15 mg ertugliflozin arm to placebo |
| 8 | HbA1c <7.0% at Wk 26 | 5 mg ertugliflozin arm to placebo |
| 9 | Systolic BP | 15 mg ertugliflozin arm to placebo |
| 10 | Systolic BP | 5 mg ertugliflozin arm to placebo |
| 11 | Diastolic BP | 15 mg ertugliflozin arm to placebo |
| 12 | Diastolic BP | 5 mg ertugliflozin arm to placebo |
| *Except for HbA1c <7.0% at Wk 26 endpoint | | |

Starting with the first hypothesis, the test will be conducted at a 5% level of significance. If the hypothesis test is significant, then the next hypothesis will be tested at a 5% level of significance. Otherwise, testing ceases within this hierarchy.

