9.2.3. Analysis of Other Secondary Endpoints

9.2.3.1. Analysis of BMD

The changes in BMD from Baseline to Week 26 at the lumbar spine, femoral neck, total hip, and distal forearm will be key safety endpoints. A BMD analysis set will be defined to include all randomized subjects who have received at least one dose of investigational product and have at least one measurement of BMD at any time during Phase A of the trial including baseline and post-baseline time points. For analyses of changes in BMD, measurements obtained post glycemic rescue therapy will be utilized if available; however BMD measurements will be censored at the point of a subject taking BMD rescue therapy.

Changes from Baseline to Week 26 in BMD will be analyzed by fitting a constrained longitudinal data analysis model with terms for treatment, visit, treatment by-visit interaction and menopausal status randomization stratum. Least-squares means and 95% confidence intervals will be used to estimate the treatment effect (difference between ertugliflozin and placebo) at Week 26.

Analyses of BMD will also be conducted separately for the male and female subgroups and also for subjects who completed ≥ 20 weeks of study treatment. Another sub-group analysis will be conducted separately for women post-menopausal for ≥ 3 years after LMP

090177e1848ce2dd\Approved\Approved On: 23-Sep-2013 15:48

(approximately 50% of the overall study population). Descriptive statistics will also be provided for each of the four randomization strata.

Changes from baseline in other continuous endpoints (including bone biomarkers) will be summarized descriptively (including 95% confidence intervals for BMD endpoints) by treatment group (for all treatment arms in each phase) and time point. Categorical endpoints will be summarized using frequency tables for each treatment group and time point.

Bone biomarker data and PTH data will be censored from the analysis if the samples were collected >7 days from the last dose of investigational product. Data for these markers will also be censored for subjects who initiate rescue medication with any bone-active medication.

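### The HbA1c <7% test at Week 26 (hierarchy steps 7 and 8) has no stated rule for missing or rescue-censored values; imputing from interim visits would be a cheap improvement

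*Combined protocol and SAP*

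**What the plan says.** Section 9.2.2 states that the proportion reaching HbA1c below 7% "at Week 26 will be analyzed using a logistic regression model with terms for treatment (categorical), Baseline HbA1c (continuous"; the synopsis gives the same two-term model. The comparison is step 7 (15 mg) and step 8 (5 mg) of a fixed sequence. Systolic pressure (steps 9 and 10) and diastolic pressure (steps 11 and 12) follow, and testing stops at the first failure.

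Section 9.2 defines the Full Analysis Set (FAS) per endpoint as treated randomized subjects who "have at least one measurement of the respective endpoint at any time during Phase A of the trial including baseline and post-baseline time points", so a baseline value alone is enough. It then says that data after rescue from "subjects who require rescue therapy prior to week 26 will be censored from primary and secondary endpoint efficacy analyses".

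Missing or post-rescue data are addressed specifically in two other places:
- For the primary endpoint, Section 9.2.1 says "No explicit imputation of missing assessments will be performed" in the constrained longitudinal (cLDA) model, with a last-observation-carried-forward ANCOVA as a sensitivity analysis. Section 9.2.2 extends the cLDA approach to FPG, body weight and blood pressure, but not to the responder endpoint.
- For bone density, Section 9.2.3.1 says "measurements obtained post glycemic rescue therapy will be utilized if available".

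Section 3 and the synopsis say that withdrawn subjects who may lack Week 26 HbA1c are still to be included in the analysis, without giving a method. Section 9 leaves detailed methodology to a separate SAP and adds "This document may modify the plans outlined in the protocol". That SAP is not in the supplied text.

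**The concern.** A logistic regression with one Week 26 outcome and only treatment and baseline HbA1c as terms cannot use a subject who has no Week 26 outcome. Fitted as written, it drops every FAS subject who was rescued or withdrew before Week 26. The cLDA keeps those subjects through their earlier visits, so the two HbA1c analyses would rest on different subjects.

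The loss is not random. Under Section 5.6, rescue in Phase A follows a confirmed high FPG, so censoring removes the subjects least likely to be below 7%. Section 9.1 shows that the plan expects this: HbA1c loss is set at 20% and bone density loss at 15% because only the former is censored at rescue.

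At stake are the reported response rates, the odds ratio, the power at steps 7 and 8, and through the hierarchy whether the blood pressure tests are reached. The primary HbA1c tests are not affected.

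**Working it through.** **1. The plan's own power figure.** Inputs from Section 9.1: difference 0.5%, SD 1.0%, 200 per arm, loss up to 20%, two-sided 0.05. Evaluable per arm: 200 × 0.80 = 160. Standard error = 1.0 × √(2/160) = 0.1118; 0.5/0.1118 = 4.47; power = Φ(4.47 − 1.96) = 99.4%. For both doses with a shared placebo arm (correlation 0.5), power is 98.9%. The stated figures are at least 99% and 98%, so they reproduce. The plan states no power for the HbA1c <7% test.

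**2. Size of the loss.** 200 × 0.20 = 40 per arm, or 120 of 600, could have no outcome in the logistic model.

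**3. Effect of dropping them.** The documents give neither response rates nor rescue rates by arm, so these are assumed. The simulation used 1,500 trials per scenario and 200 per arm, with these inputs:
- Baseline HbA1c N(8.1, 0.9) truncated to 7.0–10.5; SD of Week 26 change 0.99; placebo change −0.1.
- Correlations of 0.6–0.8 between changes at different visits.
- FPG = 28 × HbA1c + constant + noise (SD 22 mg/dL); rescue when FPG exceeds 270, 240 or 200 mg/dL at Week 6, 12 or 18; 15% random withdrawal.
- Imputation by arm from baseline HbA1c, interim HbA1c and stratum, with 15 imputations.

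The truth is the Week 26 value had there been no rescue or withdrawal. Odds ratios are adjusted for baseline HbA1c, so they exceed the crude ratios of the rates shown.

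Difference 0.5%, rescue 9.0% placebo and 4.5% ertugliflozin. Implied loss: 1 − 0.85 × 0.910 = 22.7% and 1 − 0.85 × 0.955 = 18.8%, close to the planned 20%.

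| Handling | Placebo | Ertugliflozin | Odds ratio | Step 7 power |
|---|---|---|---|---|
| Truth | 17.0% | 29.6% | 2.43 | – |
| Complete-case | 18.6% | 30.9% | 2.37 | 83.9% |
| Multiple imputation | 17.0% | 29.6% | 2.43 | 89.7% |
| Missing = non-responder | 14.4% | 25.1% | 2.26 | 83.3% |

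Complete-case raises the rates by 18.6 − 17.0 = 1.6 and 30.9 − 29.6 = 1.3 points. It costs 89.7 − 83.9 = 5.8 points of power.

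A second set of assumed inputs, with loss of about 27% and 21%, gave complete-case odds ratio 2.40 against a true 2.53 with 83% power. Imputation gave 2.52 and 91%, a gap of 8 points.

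At a 0.7% difference, with the first set's lower rescue setting, power is 99.1% complete-case and 99.5% imputed, a gap of 0.4 points. With no effect, rejection is 4.8% and 5.0% complete-case at the two rescue settings simulated, and 3.4% and 3.7% imputed. Monte Carlo standard error is about 0.9 points for power near 85% and 0.6 points for rejection near 5%.

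**4. The direction is not fixed.** Suppose all rescued subjects are non-responders, rescue is 5% in both arms, and the true rates are 20% and 35%. Complete-case gives 0.20/0.95 = 21.1% and 0.35/0.95 = 36.8%. That is 15.8 points instead of 15, so here the difference is overstated.

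**5. How far the open choice can move the result.** Assume 15% and 30% response among subjects with data. The crude complete-case odds ratio is (0.30/0.70)/(0.15/0.85) = 2.43. Counting missing as non-responder gives:
- 20%/20% missing (placebo/ertugliflozin): 12% v 24%, odds ratio 2.32.
- 30%/15% missing: 10.5% v 25.5%, odds ratio 2.92.
- 15%/30% missing: 12.75% v 21%, odds ratio 1.82, with power 60% against 89% for complete cases.

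**6. Stratum term.** If the menopausal-status stratum shifts HbA1c change by 0.4%, adding it moves imputed power from 87.9% to 88.8%. If the stratum has no effect, adding it changes nothing.

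**The case against.** The strongest reply is that silence in a protocol does not show that the plan lacks a rule. Section 9 sends detailed methods to an SAP, and missing-data handling for a secondary endpoint is exactly what an SAP would carry. This stands. A reader might infer that the plan prescribes a complete-case analysis; the documents do not say so. It is what results if the model is run literally, and the inclusion statement in Section 3 points the other way. That statement gives no method, though, and can be read as meaning the primary analysis only. Section 9 also requires a protocol amendment only for major changes to the primary endpoint or its analysis, so the protocol does not settle this choice.

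The second reply is that the effect is small. Phase 2 placebo-adjusted HbA1c reductions (Section 1.3) were 0.62 to 0.72, and near 0.7 little power is lost. This also stands. A heavier rescue setting (20.2% and 11.6%) makes the loss look larger: complete-case power 79.5% against 89.0% at 0.5%, and 98.3% against 99.7% at 0.7%. But it implies missingness of 1 − 0.85 × 0.798 = 32.2% and 1 − 0.85 × 0.884 = 24.9%, well beyond the planned 20%, so the conclusion does not rest on it.

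Third, the simulated data are approximately missing at random by construction, which favours imputation. That is true, and it limits how exactly the gain can be stated. Finally, leaving a stratum out of a logistic model is not an error. Agreed; adding it is an alignment with the cLDA.

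**Conclusion.** The point holds as a minor to moderate improvement. The supplied text leaves open how a confirmatory responder test treats up to 20% of subjects, and the model as written would drop them. On assumed inputs with loss near or somewhat above plan, dropping them raises response rates by about 1 to 2 points and slightly understates the odds ratio when placebo is rescued more. It costs roughly 6 to 8 points of step 7 power at 0.5%, and about 1 point or less at 0.7%.

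Three stronger conclusions might be drawn, and none is supported:
- That the test is invalid: simulated rejection under no effect stays near 5%.
- That dropping subjects favours ertugliflozin, or favours placebo, as a rule: the direction depends on who is lost in which arm.
- That the stated power is wrong: it refers to the primary endpoint and reproduces.

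The missing rule is a matter of text and needs no assumption, subject to the unseen SAP. The sizes depend on assumed response rates, rescue split and correlations, so confidence in them is moderate.

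**What to change.** In Section 9.2.2, or by citing the SAP section if it already covers this:
- Analyse HbA1c <7% at Week 26 on the full FAS. Multiply impute missing or rescue-censored Week 26 HbA1c by arm from baseline and interim HbA1c (already scheduled at Weeks 6, 12 and 18), dichotomise, fit the logistic model and combine by Rubin's rules.
- Add the menopausal-status randomization stratum to the logistic model, as in the cLDA. The gain is small and the cost negligible.
- Report non-responder counting as a sensitivity analysis only. In the scenario near the planned loss it lies further from the truth than complete-case (odds ratio 2.26 against 2.37, truth 2.43).
- Fix the imputation model before Phase A unblinding, since Sections 5.2 and 9.4 open Phase A results to limited sponsor staff after database lock while Phase B continues.

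The cost is wording and some programming, with no new data. The downsides are slightly lower reported response rates than complete-case and a slightly conservative test under the null (3.4% to 3.7% in the simulation).

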9.2.3. Analysis of Other Secondary Endpoints

9.2.3.1. Analysis of BMD

The changes in BMD from Baseline to Week 26 at the lumbar spine, femoral neck, total hip, and distal forearm will be key safety endpoints. A BMD analysis set will be defined to include all randomized subjects who have received at least one dose of investigational product and have at least one measurement of BMD at any time during Phase A of the trial including baseline and post-baseline time points. For analyses of changes in BMD, measurements obtained post glycemic rescue therapy will be utilized if available; however BMD measurements will be censored at the point of a subject taking BMD rescue therapy.

Changes from Baseline to Week 26 in BMD will be analyzed by fitting a constrained longitudinal data analysis model with terms for treatment, visit, treatment by-visit interaction and menopausal status randomization stratum. Least-squares means and 95% confidence intervals will be used to estimate the treatment effect (difference between ertugliflozin and placebo) at Week 26.

Analyses of BMD will also be conducted separately for the male and female subgroups and also for subjects who completed ≥ 20 weeks of study treatment. Another sub-group analysis will be conducted separately for women post-menopausal for ≥ 3 years after LMP

090177e1848ce2dd\Approved\Approved On: 23-Sep-2013 15:48

(approximately 50% of the overall study population). Descriptive statistics will also be provided for each of the four randomization strata.

Changes from baseline in other continuous endpoints (including bone biomarkers) will be summarized descriptively (including 95% confidence intervals for BMD endpoints) by treatment group (for all treatment arms in each phase) and time point. Categorical endpoints will be summarized using frequency tables for each treatment group and time point.

Bone biomarker data and PTH data will be censored from the analysis if the samples were collected >7 days from the last dose of investigational product. Data for these markers will also be censored for subjects who initiate rescue medication with any bone-active medication.

